5.3. ANALYSES OF SECONDARY OUTCOMES

All continuous secondary outcomes at 5 years will be analysed in the same manner as described in Section 5.2 for the primary outcome. Some outcomes may exhibit skewed distributions. However, as long as the skewness is not severe, comparison of mean responses on their original scale is reasonable, more readily interpretable, and consistent with the way in which clinicians think about these measures in practice. If skewness is severe appropriate transformations of the data will be done prior to fitting these models.

All binary neurodevelopmental secondary outcomes at 5 years will be analysed using generalised linear models (GLM) with binomial link function in order to enable estimation of risk ratios. In case of non-convergence of the model parameters one of the following solutions will be pursued (in this order): site will be replaced with country in the models; binary logistic regression models will be fitted and marginal risk ratios with bootstrap 95% confidence intervals will be computed; or Poisson link functions will be used. The margins command in Stata will also be used to estimate risk differences with 95% confidence intervals. In analogy to the linear regression model, the respective GLM models will include the factor variables anaesthesia arm (factor levels: GA and RA), gestational age (factor levels: 182 to 209 days, 210 to 258 days and >= 259 days) as fixed effects and site as a random effect (or country as a fixed effect).

6. STATISTICAL ISSUES

All analyses will be done in Stata (version 14.2 or higher) and all confidence intervals and p-values will be 2-sided.

6.1. HANDLING OF MISSING DATA

Statistical analysis approaches and imputation techniques can never compensate for or exactly reproduce missing data. Therefore, no analytical strategy exists that can minimise all bias potentially introduced by missing data. However, consistencies or inconsistencies in the results based on different strategies to handle missing data can provide support for the interpretation of the study findings and either strengthen or qualify the study conclusions.

Allowing for missing values using multiple imputation:

Assuming validity of the MAR assumption, fully conditional modelling will be used to multiply impute missing values based on variable-specific prediction models. In particular, multivariate imputation chained equations (MICE) will be used to perform imputation of missing values. Depending on the type of outcome, different link functions and model specifications will be employed to utilise the built-in imputation: predictive mean matching under a Gaussian model for continuous data, logistic regression for binary data, polytomous logistic regression for unordered categorical data and proportional odds models for ordered categorical data.

Statistical Analysis Plan

If MICE models do not converge missing values will be filled in using multivariate normal regression (MVN). These two methods have been shown to give broadly equivalent results.

A total of 20 imputed data sets will be generated based on the MICE algorithm. For each of the respective data sets, the outcome-specific effect estimate and standard error will be computed and pooled using Rubin's rules (Van Buuren, 2007).

In the analysis of the 5-year data of the GAS study, the variables used in the multiple imputation models will include baseline, post-randomisation, 2 year cognitive variables and 5 year outcome variables. The following prespecified variables will be used as predictor variables within the imputation approach (since most of these variables also have missingness, they will also be imputed where necessary):

Baseline: anaesthesia group, country, site (if possible), sex, gestational age at birth (categorised), birth weight, mother received antenatal steroids, mother's education, maternal age < 21

Surgery: need for fluid bolus for hypotension, duration of surgery, significant postoperative apnoea, age at surgery

- **2 years:** composite cognitive, language, motor and social-emotional score of the Bayley scales of infant and toddler development, any additional anaesthetic exposures since the inguinal herniorraphy, any interventions for neurodevelopmental problems, any other neurological abnormality
- **5 years:** Full Scale IQ score, verbal IQ, performance IQ and processing speed quotient of the WPPSI; any chronic illness, any additional anaesthetic exposures since the inguinal herniorraphy, total length of any readmission to hospital, cerebral palsy, any interventions for neurodevelopmental problems, any other neurological abnormality.

With additional missing data at 5 years convergence problems, especially with some binary variables with low prevalence, may occur when doing multiple imputations. If these convergence problems are experienced some of the variables specified will be excluded from the imputation models. None of the variables required to ensure congeniality with the analysis models will be removed from the imputation models.

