2.4. SAMPLE SIZE

The sample size was based on the 5 year follow up neurodevelopmental outcome. The WPPSI-III full scale IQ score is a standardised score with a mean of 100 and standard deviation of 15. A difference of 5 points (1/3 of a standard deviation) will be taken as the largest difference that would be acceptable to demonstrate equivalence.

The planned sample size was chosen so that if the two methods of anaesthesia really were equivalent and we assumed an expected difference of only 1 standardised score point, there was a 90% chance that a 95% confidence interval will exclude a difference of more than 5. With these assumptions, the trial would need 598 infants in total. The planned sample size of 660 allowed for 10% loss to follow-up. The enrolment target was increased to enable replacement of participants who were excluded due to major protocol violations.

Statistical Analysis Plan

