4. OUTCOME VARIABLES

4.1. PRIMARY OUTCOME AT AGE 5 YEARS

The primary outcome is the Full Scale IQ score of the Wechsler Preschool and Primary Scale of Intelligence, Third Edition (WPPSI-III) at 5 years chronological age. Verbal, visuo-spatial and processing speed skills are incorporated into the Full Scale IQ score, which is indicative of general intellectual ability.

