 - 5.1 The Global Executive Composite (GEC, T score) of the Behaviour Rating Inventory of Executive Function Preschool Version Parent Form (BRIEF-P) to measure behavioural executive abilities
 - 5.2 The Global Adaptive Composite (GAC, composite score) of the Adaptive Behavior Assessment System Second Edition (ABAS-II) to measure the child's adaptive behavior
 - 5.3 The Child Behaviour Checklist Caregiver Questionnaire (CBCL) to measure behavioural problems consisting of
 - 5.3.1 The Total Problems Score (T score)
 - 5.3.2 CBCL internalising problems T score
 - 5.3.3 CBCL externalising problems T score
- 6. Developmental issues
 - 6.1 Any developmental issue (any of the below)
 - 6.2 Child has speech or language issues / interventions*
 - 6.3 Child has psychomotor issues / interventions*
 - 6.4 Child has global developmental delay*
- 7. Behavioural disorders
 - 7.1. Any behavioural disorders (any of the below or oppositional defiant disorder)
 - 7.2. Child has been diagnosed with Attention Deficit Hyperactivity Disorder (ADHD)*
 - 7.3. Child has been diagnosed with Autism Spectrum Disorder (ASD) *
- 8. Physical disability
 - 8.1. Child has a hearing abnormality
 - 8.1.1. Child has a hearing aid*
 - 8.2. Child has a visual defect in either eye
 - 8.2.1. Child is legally blind*
 - 8.3. Child has cerebral palsy
- 9. Parents' awareness of group allocation*
- 10. Awareness of group allocation by Psychologist / Paediatrician*
- * These variables will be summarised using descriptive statistics by treatment arm only. No treatment effect or confidence intervals will be calculated.

Version 1 Page 7

Statistical Analysis Plan

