5.2. ANALYSES OF PRIMARY OUTCOME VARIABLE

Descriptive summary statistics for the primary outcome variable at 5 years chronological age will be reported.

Version 1

Statistical Analysis Plan

Linear regression will be used to analyse the Full Scale IQ score of the WPPSI-III at 5 years. The model will include the factor variables anaesthesia arm (factor levels: GA and RA), gestational age at birth (factor levels: "182 to 209 days", "210 to 258 days" and ">= 259 days") as fixed effects and site as a random effect. If the model does not converge (e.g. because of small numbers in some sites) consideration will be given to replacing site in the model with country as a fixed effect.

The analysis will be conducted for the PP and the ITT populations. The analyses will be repeated for the subset of participants with follow-up data at 5 years as well as using multiple imputation to handle the cases lost to follow-up under the MAR assumption. The primary analysis will be based on the PP population and the multiple imputation analysis method because this is an equivalence study. A PP analysis is likely to give a more conservative estimate (in the direction of non-equivalence) of the true causal effect.

The model coefficient for the anaesthesia treatment effect (conditional mean difference) will be computed along with a two-sided 95% confidence interval. Equivalence will be accepted if this confidence interval excludes values less than -5 points and values greater than +5 points.

Loss to follow-up will be investigated by providing a table with summary statistics by treatment arm for participants who attended and did not attend the 5 year visit. Variables included in this table will include key baseline variables as well as the composite cognitive, language, motor and social-emotional score of the Bayley scales of infant and toddler development measured at the 2-year time point.

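### The SAP sets no rule for children who attend at 5 years but cannot complete the WPPSI-III because of impairment, and neither planned analysis can show the effect of that missingness

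*SAP*

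**What the plan says.** - **Primary analysis.** Section 5.2 analyses Full Scale IQ in the per-protocol and ITT populations, once in children with 5-year data and once "using multiple imputation to handle the cases lost to follow-up under the MAR assumption". The per-protocol analysis with multiple imputation is primary.
- **Imputation.** Section 6.1 covers missing values in general. Continuous variables are imputed by "predictive mean matching under a Gaussian model for continuous data", with a multivariate normal model as fallback if the chained equations do not converge.
- **Predictors.** Among others, section 6.1 lists four 2-year Bayley composites and, at 5 years, the three other WPPSI scores, chronic illness and "cerebral palsy, any interventions for neurodevelopmental problems, any other neurological abnormality". Predictors not needed for congeniality may be dropped if convergence fails.
- **Recorded impairment.** Section 4.2 lists items such as "Child has global developmental delay", autism spectrum disorder, legal blindness, hearing abnormality and hearing aid. None of these is named as an imputation predictor.
- **Sensitivity.** Section 6.2 offers complete case and multiple imputation, and nothing that departs from MAR.
- **Silence.** No section says how a child who attends but cannot be tested is classified or scored.

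**The concern.** Full Scale IQ comes from a test the child must be able to sit. A child with severe delay or severe autism may attend the visit and still have no score. That score is missing because of the outcome itself, which is where MAR is least plausible. Section 6.1 nevertheless treats it like the missing score of a family that moved away.

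Section 6.1 says that agreement between missing-data strategies can strengthen the conclusions. Agreement gives no reassurance here. Complete case leaves the child out, and predictive mean matching gives the child a score observed in someone who could be tested. Both rest on tested children only. The loss-to-follow-up table in 5.2 would not reveal the problem either, because it compares attenders with non-attenders and these children attended.

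At stake is the equivalence conclusion. If severe impairment is more frequent in one arm, part of that difference may be missing from the comparison of means.

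**Working it through.** **1. Reproduce the plan's own figure.** Inputs from SAP section 2.4: IQ is a "standardised score with a mean of 100 and standard deviation of 15"; the margin is 5 points; "we assumed an expected difference of only 1 standardised score point"; power is 90% with a 95% confidence interval.

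n per arm = 2 × 15² × (1.960 + 1.282)² / (5 − 1)² ≈ 296, or 592 in total. Requiring both margins to be excluded gives 298 per arm (596). A t-based calculation gives 299 per arm, which matches the stated 598.

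With 299 per arm, SE = 15 × √(2/299) = 1.227.

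**2. Shift in the treatment difference.** Let p₁ and p₂ be the untestable shares in the two arms, and let the gap be the mean imputed score minus the level these children would have scored.

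Shift = (p₁ − p₂) × gap.

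If p₁ = p₂ the shift is zero, however large the gap. The SAP gives neither the shares nor the gap, so the values below are assumptions.

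| Imbalance | Gap 15 | Gap 45 |
|---|---|---|
| 1 percentage point (about 3 children of 299) | 0.15 | 0.45 |
| 2 percentage points (about 6 children of 299) | 0.30 | 0.90 |

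**3. Is a gap of 15 to 45 plausible when the imputation uses informative predictors?** A small simulation of predictive mean matching was run with 598 children and these assumptions: tested children have mean 100 and SD 15; untestable children have a latent mean of 45; one 2-year predictor has mean 60 in the untestable and correlates 0.5 or 0.7 with IQ in the others.

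- Correlation 0.5: imputed mean about 82, gap about 37.
- Correlation 0.7: imputed mean about 75, gap about 30.

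Most of this gap comes from MAR and little from the limit to observed donors. The regression prediction at a predictor value of 60 is 100 + 0.5 × (60 − 100) = 80, or 100 + 0.7 × (60 − 100) = 72. Under these assumptions the multivariate normal fallback would still leave gaps of about 35 and 27. The real model has more predictors than this one, so its gap could be smaller.

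**4. Effect on the conclusion.** Suppose the true difference is exactly 5 and the shift b is towards zero. The chance of accepting equivalence is Φ(b/1.227 − 1.96).

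| b | Calculation | Chance of accepting |
|---|---|---|
| 0 | Φ(−1.96) | 2.5% |
| 0.15 | Φ(0.12 − 1.96) | 3.3% |
| 0.30 | Φ(0.24 − 1.96) | 4.3% |
| 0.45 | Φ(0.37 − 1.96) | 5.6% |
| 0.90 | Φ(0.73 − 1.96) | 11.0% |

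If the excess of untestable children lies in the arm with the higher mean, b has the opposite sign. The observed difference then widens and equivalence becomes harder to accept.

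**The case against.** A reader might infer that the SAP prescribes replacing the worst outcomes with better scores and so pushes the trial towards equivalence. The text does not support that, for four reasons.

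- **The SAP is silent on these children.** Section 5.2 ties the imputation to loss to follow-up, and their imputation follows only from the general wording of 6.1. A scoring rule may exist in the protocol, which is not at hand. This stands, and it makes the point a gap in the rules. Since 6.1 fixes the primary imputation in detail, the rule should be stated or cross-referenced there.
- **Matching is not to tested children at large.** It uses Bayley composites, interventions, cerebral palsy, other neurological abnormality and, for a child who completed part of the WPPSI, that child's own subscores. This stands: it reduces the gap, but step 3 of the working suggests it does not remove it.
- **Numbers may be small.** Section 2.3 excludes infants with recognised risk factors for adverse neurodevelopment and those born before 26 weeks. The 11.0% figure needs about six more untestable children in one arm, a 45-point gap, the adverse direction and a true difference exactly at the margin. This stands.
- **Impairment stays visible elsewhere.** Section 4.2 reports several conditions by arm, compares composites such as any developmental issue, and includes caregiver-rated scales that need no testing of the child. An imbalance could show there. That would not correct the primary estimate, and global delay, autism and legal blindness are descriptive only.

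**Conclusion.** The point holds as a gap in the missing-data rules. As written, 6.1 sends an untestable attender to MAR imputation from tested children, the complete-case analysis drops that child, and no planned analysis tests the assumption. Recorded variables that bear directly on the missingness are left out of the imputation model.

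The size is conditional. The shift is zero with equal untestable shares, and about 0.15 to 0.9 points under assumed imbalances of 1 to 2 percentage points and gaps of 15 to 45 points. Against a margin of 5 this is modest, though at the upper end it matters for a difference near the margin. The documents do not show that any such imbalance exists or which way it would run.

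It might also be inferred that these children should receive the lowest attainable IQ in the primary analysis. That goes too far. Blindness or cerebral palsy can prevent testing without establishing low intellect, so a mandatory floor would replace one untested assumption with a harsher one. A low-score rule belongs in a sensitivity analysis.

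**What to change.** 1. **Sections 5.2 and 6.1:** define a category *attended, untestable because of impairment*, separate from *not assessed*, and report numbers and reasons by arm. If the protocol already has a scoring rule, cite it.
2. **Section 6.2:** prespecify a sensitivity analysis that gives these children a low Full Scale IQ, either the lowest attainable score or the imputed score reduced by a stated range of deltas, such as the 15 to 45 points used here. The primary analysis stays as it is.
3. **Section 6.1:** add global developmental delay, autism, legal blindness and hearing impairment at 5 years to the imputation predictors, or one composite of them if prevalence is low, subject to the existing convergence rule.

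**Cost:** SAP wording, one derived variable and one further analysis, with no change to the sample size. The SAP lists no variable for why a WPPSI was not completed, so the derivation depends on the assessment records holding the reason. Rare binary predictors may cause convergence trouble, which the composite is meant to limit. Low scores will slightly widen the interval in the sensitivity analysis.

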4.3. OTHER SECONDARY OBJECTIVES (ALREADY REPORTED)

The trial also had the following secondary outcomes that were assessed at time points other than 5 years:

- 1. Compare a range of secondary neurodevelopmental measures between groups at 2 years (corrected). These included:
 - the cognitive, motor and language scales of the Bayley Scales of Infant & Toddler Development-III (Bayley-III)
 - social-emotional scale and adaptive behavior scale from the Bayley-III
 - the MacArthur-Bates Communicative Development Inventory
- 2. A paediatric assessment including a neurological examination to determine the presence of cerebral palsy conducted by a paediatrician blinded to the type of anaesthetic used.
- Describe the frequency and characteristics of apnoea in the postoperative period after both regional and general anaesthesia for inguinal hernia repair in infants and determine other factors associated with increased risk of apnoea.

These secondary endpoints have already been analysed when the 2-year database was locked and has been published previously (Davidson, 2016; Davidson, 2015).

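### The imputation list in SAP Section 6.1 omits the 2-year cerebral palsy finding, so a known case lost at 5 years may be imputed as unaffected

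*SAP*

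**What the plan says.** SAP Section 6.1 fixes in advance the variables for the chained-equations imputation. The 2-year variables are the "composite cognitive, language, motor and social-emotional score of the Bayley scales of infant and toddler development", followed by "any additional anaesthetic exposures since the inguinal herniorraphy, any interventions for neurodevelopmental problems, any other neurological abnormality". The 5-year variables include "total length of any readmission to hospital, cerebral palsy, any interventions for neurodevelopmental problems, any other neurological abnormality". Listed variables are both predictors and targets: "since most of these variables also have missingness, they will also be imputed where necessary". Binary variables are imputed by logistic regression.

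Section 4.3 lists, among outcomes not measured at five years, "A paediatric assessment including a neurological examination to determine the presence of cerebral palsy", done by a blinded paediatrician. It closes with "These secondary endpoints have already been analysed when the 2-year database was locked".

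Section 4.2 lists "8.3. Child has cerebral palsy" without an asterisk, so a treatment effect is to be estimated. Only five binary outcomes are unstarred (6.1, 7.1, 8.1, 8.2, 8.3), and cerebral palsy is the only one of these five named in the imputation list.

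**The concern.** The 5-year cerebral palsy value is missing for the children who miss the 5-year visit. For those seen at 2 years, the most direct information on that value is the 2-year examination for the same condition. The trial holds it, but the list leaves it out and relies on proxies: Bayley scores, interventions and a residual neurological item.

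In the 5-year list cerebral palsy stands beside that residual item, so there the word 'other' means other than cerebral palsy. If the 2-year item has the same meaning, a child whose only neurological finding at 2 years is cerebral palsy enters the imputation model with no neurological abnormality recorded.

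At stake are the risk ratio and risk difference for outcome 8.3. Events are likely to be few, so a single misimputed child is visible. The missing-at-random assumption is also more plausible for this outcome when the child's 2-year cerebral palsy status is conditioned on.

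**Working it through.** **Inputs.** From SAP Section 2.4: 660 infants and 10% loss to follow-up. From Section 2.1: 1:1 allocation, so 330 per arm. The SAP gives no prevalence of cerebral palsy, no proxy strength and no loss by cerebral palsy status, so it has no figure on this point to reproduce. All other inputs below are assumptions.

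**Step 1: how well can the listed proxies recover a known case?** For an affected child, the probability of being imputed as affected is

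logit P = logit(prevalence) + sum of the log likelihood ratios of the proxies.

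The proxies were a motor deficit, a smaller additional cognitive deficit, and interventions in affected versus unaffected children. With ideal use of these proxies and no 2-year finding, the average of P over affected children is:

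| Motor deficit; interventions | 1% prevalence | 2% | 3% |
|---|---|---|---|
| 1 SD; 60% v 20% | 0.05 | 0.09 | 0.12 |
| 1.5 SD; 80% v 15% | 0.19 | 0.28 | 0.34 |
| 2 SD; 90% v 15% | 0.36 | 0.46 | 0.52 |
| 2.5 SD; 95% v 10% | 0.61 | 0.68 | 0.73 |
| 3 SD; 95% v 10% | 0.74 | 0.80 | 0.83 |

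**Step 2: simulated logistic imputation.** N = 660, 20% missing at 5 years, 20 draws, and a 2-year finding assumed 90% sensitive and 99.9% specific. The table gives the probability that a lost child with cerebral palsy at both ages is imputed as affected, over prevalences of 1-3%:

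| Proxies | Without 2-year finding | With it |
|---|---|---|
| Weak (1 SD) | 0.06-0.13 | 0.73-0.89 |
| Middle (2 SD) | 0.31-0.50 | 0.78-0.92 |
| Strong (3 SD) | 0.62-0.76 | 0.83-0.93 |

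A second simulation assumed 2% prevalence, 80-95% of 2-year cases still positive at 5 years, a mean motor score of 65-75 against 97, and interventions in 80-90% against 20%. It gave 0.15-0.38 without and 0.74-0.91 with the finding. Adding the finding helped in every scenario. Both simulations used only some of the listed predictors.

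The gain depends on the accuracy of the 2-year examination. Used alone, the finding has predictive value p·se / [p·se + (1-p)(1-sp)]. At p = 1%, se = 80% and sp = 99.5% this is 0.008/(0.008 + 0.00495) = 0.62. At p = 3%, se = 90% and sp = 99.9% it is 0.965.

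**Step 3: number of children.** At 2% prevalence and 90% sensitivity, 660 × 0.02 × 0.9 = 11.9 known cases. With 20% loss, 2.4 are lost. The gain in probability at 2% prevalence is 0.841 - 0.098 = 0.743 (weak), 0.873 - 0.425 = 0.448 (middle) and 0.890 - 0.716 = 0.174 (strong). That is 1.8, 1.1 and 0.4 children per imputed data set. With the planned 10% loss, 1.2 are lost and the gains halve to about 0.9, 0.5 and 0.2. If 40% of affected children were lost, about 5 of 13 would be concerned (660 × 0.02 = 13.2; × 0.40 = 5.3).

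**Step 4: effect on the risk difference.** In the second simulation the error against complete data (RMSE) fell from 0.33-0.69 to 0.20-0.40 percentage points. The sampling error is √(2 × 0.02 × 0.98 / 330) = 1.09 points. Added in quadrature, assuming independence:

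- lower end: √(1.09² + 0.33²) = 1.14, falling to √(1.09² + 0.20²) = 1.11
- upper end: √(1.09² + 0.69²) = 1.29, falling to √(1.09² + 0.40²) = 1.16

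**The case against.** Several points on the other side are fair.

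- **The proxies may be good enough.** The list keeps the Bayley motor score, interventions and the residual neurological item, plus perinatal variables that the simulations left out. A reader might infer that a lost known case will mostly be imputed as unaffected. The SAP does not support that: with strong proxies such a child is imputed as affected more often than not. What stands is that recovery improved in every scenario.
- **Imputation of 8.3 is inferred.** Section 5.3 carries the Section 5.2 methods over expressly for continuous outcomes only, and its binary paragraph does not mention imputation. Sections 6.1 and 6.2 make imputation the likely reading, because 5-year cerebral palsy is listed, binary data have an imputation model, and both complete-case and imputed analyses are announced. The point is conditional on that reading.
- **'Other' is undefined.** The 2-year list has no cerebral palsy item for it to contrast with, so it may include cerebral palsy. The two lists would then use one phrase in two senses, and the wording would still need clarifying.
- **Agreement of the two analyses.** A reader might infer that complete-case and imputed results would share the same error and so agree. This was not shown, and since the proxies move imputation toward the truth, the results need not coincide.
- **Limited reach.** Children who also missed the 2-year assessment gain nothing. Section 4.2 already says that secondary outcomes will be read with caution.

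**Conclusion.** The omission stands on the text: the trial holds a 2-year cerebral palsy finding, the prespecified list leaves it out, and 5-year cerebral palsy is both an imputed variable and an outcome with an estimated effect. If 8.3 is analysed by multiple imputation, a known case lost at 5 years may be imputed as unaffected: often if the proxies are weak, less often if they are strong.

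The practical size is small. About one known case is lost at the planned 10% loss and a few under heavier loss, and total error in the risk difference falls by 0.03 to 0.13 percentage points. These sizes rest on an assumed prevalence near 2% and assumed proxy strength, persistence and accuracy of the 2-year finding. The effect on Full Scale IQ was not computed. It should be small, because few children are involved and the Bayley scores already inform IQ. The primary equivalence conclusion is not in question.

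**What to change.** In Section 6.1, add *cerebral palsy (2-year paediatric assessment)* to the 2-year predictor list. State that 5-year cerebral palsy is imputed by logistic regression with augmentation (the augment option in Stata), so that near-perfect prediction does not halt the chain. If the model still does not converge, the existing rule in Section 6.1 for dropping variables applies, and no special protection is needed.

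The cost is a few words in the SAP and no new data collection. The small downside is a rare, near-deterministic predictor in the chain, which the augmentation is meant to handle.

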6.3. SUBGROUP ANALYSES

Exploratory subgroup analyses will be performed for the primary outcome variable with respect to the age at surgery (> 70 days vs <= 70 days), duration of surgery (< 2 hours vs >= 2 hours) and country. Stratified analyses will be done by repeating the same analysis as described in Section 5.2 for each of the above mentioned factors.

The assessment of treatment-by-country interaction will be made by fitting a model for the primary outcome variable. The model will include treatment arm, country, and gestational age as fixed effects as well as the interaction term country by treatment. The p-value for the country by treatment interaction will be presented.

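### The listed imputation model carries no arm interactions, so imputed data would pull the exploratory subgroup and country-by-treatment results towards homogeneity

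*SAP*

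**What the plan says.** **Imputation model (SAP Section 6.1).** The prespecified predictors include "Baseline: anaesthesia group, country, site (if possible), sex, gestational age at birth (categorised), birth weight" and "Surgery: need for fluid bolus for hypotension, duration of surgery, significant postoperative apnoea, age at surgery", together with 2-year and 5-year variables. No product of arm with another variable is listed, and nothing says that the arms are imputed separately. Twenty imputed data sets are planned. Some variables may be dropped if convergence fails, subject to the assurance that "None of the variables required to ensure congeniality with the analysis models will be removed from the imputation models".

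**Primary analysis (SAP Section 5.2).** Full Scale IQ is regressed on arm and gestational age category "as fixed effects and site as a random effect". If that model does not converge, "consideration will be given to replacing site in the model with country as a fixed effect". The per-protocol population with multiple imputation is primary; a complete-case version is also run.

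**Subgroups (SAP Section 6.3).** The Section 5.2 analysis is repeated within strata of age at surgery, duration of surgery and country. One interaction model is added, with arm, country and gestational age "as well as the interaction term country by treatment", and its p-value is to be reported. The section calls the subgroup analyses exploratory. It does not say whether the interaction model uses imputed or complete-case data.

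**The concern.** An imputation model should be at least as rich as the analyses run on its output. If IQ is imputed from arm and country as separate terms, every imputed child receives the same arm effect whatever the country, age at surgery or duration. The imputed part of the data then contains no direct effect modification, and pooling it with the observed part dilutes any that exists.

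What is at stake is the supporting evidence that the arm effect is uniform. In an equivalence trial, a dilution towards homogeneity errs in the reassuring direction.

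A second, separate matter is site. It is in the primary analysis model, so it is among the variables needed for congeniality, yet its place in the imputation model is conditional. The country fallback in Section 5.2 depends on convergence of the analysis model, not on what the imputation could include. As written, the plan allows imputing with country and analysing with site.

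**Working it through.** **Inputs from the SAP.** Total 660, 1:1 allocation, SD 15, margin 5, expected difference 1, 10% loss, 20 imputations, 28 sites, seven countries.

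**Inputs assumed.** Outcomes missing completely at random; loss of 20% or 30% as well as the planned 10%; a true 5-point difference in arm effect between two equal subgroups; a covariate unrelated to arm and correlated 0 or 0.5 with IQ; normal-model imputation in place of predictive mean matching; between-site SD 4.

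**Step 1: the plan's own figure.** Per arm, n = 2 × 15² × (1.960 + 1.282)² / (5 − 1)² = 450 × 10.51 / 16 ≈ 296, or 592 in total, against 598 stated. For 10% loss, 598 × 1.1 = 658 and 598 / 0.9 ≈ 665, against 660 stated. The inputs are consistent, and nothing below depends on this figure.

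**Step 2: expected shrinkage.** Let Δ be the true difference in arm effect between two strata and m the missing fraction. Observed children contribute Δ; children imputed without an arm interaction contribute 0. The pooled contrast is about (1 − m)Δ + m × 0 = (1 − m)Δ. With Δ = 5 this is 4.5, 4.0 and 3.5 at m = 10%, 20% and 30%.

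**Step 3: simulation of the subgroup contrast (true value 5).** The pair in each cell is for covariate correlation 0 and 0.5. The ratio divides the second column by the third, from the same simulated trials.

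| Missing | Imputed, no interaction | Imputed, with interaction | Complete case | Ratio |
|---|---|---|---|---|
| 10% | 4.38, 4.54 | 4.87, 5.05 | 4.87, 5.06 | 0.90, 0.90 |
| 20% | 3.90, 4.15 | 4.83, 5.18 | 4.84, 5.20 | 0.81, 0.80 |
| 30% | 3.50, 3.47 | 4.95, 4.94 | 4.97, 4.99 | 0.71, 0.70 |

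The ratios match 1 − m, and a covariate that only predicts IQ does not help.

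**Step 4: country-by-treatment test.** Seven countries with assumed shares of 25, 25, 20, 12, 8, 6 and 4%; Wald test on 6 degrees of freedom at 5%; 400 simulated trials. For power, the assumed arm effects by country are +5, −3, +5, −3, 0, +5 and −5 points.

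| Missing | Situation | No interaction | With interaction | Complete case |
|---|---|---|---|---|
| 10% | null | 1.5% | 4.5% | 5.0% |
| 20% | null | 0.8% | 5.8% | 5.5% |
| 30% | null | 0.0% | 5.0% | 4.2% |
| 10% | power | 49.5% | 64.5% | 63.8% |
| 20% | power | 33.2% | 62.8% | 63.5% |

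Monte Carlo standard errors are about √(0.05 × 0.95 / 400) = 1.1 percentage points near 5% and √(0.5 × 0.5 / 400) = 2.5 points near 50%. Power at 30% missing was not obtained.

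**Step 5: leaving site out of the imputation (true arm effect 1; site as fixed effects in the analysis).**

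| Missing | Estimate, site out / in | SE, site out / in | SE ratio |
|---|---|---|---|
| 10% | 0.942 / 0.949 | 1.270 / 1.262 | 1.006 |
| 20% | 0.980 / 0.973 | 1.365 / 1.345 | 1.015 |
| 30% | 0.966 / 0.966 | 1.470 / 1.446 | 1.017 |

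The estimate does not move, and the standard error rises by less than 2%.

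**The case against.** **The assurance concerns variables, and all of them are listed.** This stands. A reader might infer that the missing interactions contradict the congeniality sentence. They do not: it limits which variables may be removed, and arm, country, age at surgery and duration are all present. The SAP is silent on interactions rather than excluding them. Still, an analyst who follows the prespecified list would leave them out.

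**Optional site is not the cause.** This also stands. A reader might link the conditional wording on site to the shrinkage, but Step 5 shows no such link. Country is listed without condition. What remains is a wording conflict.

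**Only country is tested.** Correct. Age at surgery and duration receive stratum estimates without an interaction test, so no test for those factors can be biased; only the contrast that a reader draws between strata is diluted.

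**Complete-case results are also planned, and the country test may use them.** Section 6.3 does not say. Complete-case estimates are not diluted when data are missing completely at random, and Section 6.1 intends comparison across strategies. That softens the point, but imputation is primary in Section 5.2 and the data set for the test is unnamed.

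**Imputation might be rerun within each stratum.** That would remove the dilution of the stratum estimates. The SAP does not say so, and a single total of 20 data sets reads more naturally as one common imputation.

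**The 2-year scores may carry some of the effect modification.** They might. If a 2-year score correlated 0.5 with IQ showed the same standardised contrast, imputed children would contribute about 0.5 × 5 = 2.5, and the pooled value at 10% missing would be 0.9 × 5 + 0.1 × 2.5 = 4.75. Dilution would be halved, not removed.

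**Conclusion.** The point holds in limited form. With imputation as listed, and if the imputed data feed Section 6.3, subgroup contrasts are diluted by about the missing fraction: about 10%, or 0.5 of a 5-point contrast, at the planned loss. Larger dilution requires larger loss, which is an assumption. The country-by-treatment test becomes conservative and loses power; the size of that loss depends on the assumed country shares and effects.

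These analyses are exploratory. A reader might infer that the equivalence claim itself is in doubt. The SAP does not support that: equivalence is judged on the overall arm coefficient, which the missing interactions leave essentially unaffected. The conditional inclusion of site fits poorly with the congeniality assurance but has negligible numerical effect under the assumed between-site SD of 4. The changes are worth making because they are cheap, not because the main result is threatened.

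**What to change.** 1. **Section 6.1.** For the Section 6.3 analyses, impute separately by randomised arm with country, age at surgery and duration of surgery in the model, the last two including their Section 6.3 cut-points. Alternatively, add the products of arm with these three factors to the imputation model for IQ.
2. **Section 6.3.** State that the country-by-treatment test uses these imputed data, with complete case as a sensitivity analysis.
3. **Sections 5.2 and 6.1.** Use the same site or country term in the imputation and analysis models. If only country can be included in the imputation, use country in the analysis as well.

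The cost is a few lines of SAP text and a by-arm option in the imputation command. Imputation variance rises slightly because each arm is modelled on about half the children. Convergence becomes somewhat harder for low-prevalence binary variables, which Section 6.1 already allows to be dropped. If site indicators make the by-arm models too sparse, the country term in item 3 is the way out.
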